8.4. Data sources

Data sources used to construct the analysis data set for this study are presented in Table 3. Within each country, records from all registries are linkable at the individual level by a unique national person identifier. For births recorded in the birth registries, a maternal unique identifier is a variable on the record of the offspring, enabling exact linkage between a given offspring and maternal history of medication dispensing or diagnoses before or during pregnancy.

Diagnosis in all countries are registered based on the ICD-10 coding system and accessed through registers as specified in Table 3. Similarly medications are classified according to the ATC coding system and accessed through prescription registers. The medical birth registers in the included countries furthermore contain similar information other relevant covariates (calendar year of delivery, maternal age at conception, parity; marital/cohabiting status; pregravid body mass index (BMI); smoking during pregnancy; single or multiple pregnancy; and child's sex.)

Validity of routine data in Nordic national registries has been found to be high in all countries.²²⁻³⁷ In Denmark, positive predictive value of diagnoses of cardiac malformations is 89%.³⁸ For drugs used chronically, there is also high level of agreement between general practitioner and dispensing records.³⁹ An agreement between dispensing records and drug use reported in the standard medical antenatal records included in the birth register was 69% for antiepileptics in Sweden.⁴⁰

Table 3. National registries in Denmark, Finland, Norway and Sweden and type of data available from each registry

Study variable/role	Type of data	Data source(s)	Coding system(s) used
Person identification (mothers and children)	Unique personal identifier for data linkage	Danish Civil Registration System ⁴¹ Danish Civil Registration System Finnish Medical Birth Register* National Registry of Norway Swedish Total Population Register ⁴²	N/A
Study population	Pregnancies ending in singleton/multiple live birth or stillbirth	Danish Medical Birth Registry Finnish Medical Birth Register* Medical Birth Registry of Norway Swedish Medical Birth Register Danish National Patient Registry ^{43,44}	A specific variable in each birth registry
	Pregnancies ending in therapeutic 2nd trimester induced abortion	Finnish Register on Induced Abortions* Norwegian Register of Pregnancy Terminations (part of the Medical Birth Registry of Norway) Not available in Sweden	ICD-10

Table 3. National registries in Denmark, Finland, Norway and Sweden and type of data available from each registry

Study variable/role	Type of data	Data source(s)	Coding system(s) used
Exposure (for full list see Section 8.3.1)	Maternal dispensings of pregabalin, lamotrigine, duloxetine	Danish National Health Services Prescription Database ^{45,46} Finnish Prescription Register ⁴⁵ Norwegian Prescription Database ⁴⁵ Swedish Prescribed Drug Register ⁴⁵	ATC
		Outcome (for full list see Section 8.3.2)	Major congenital malformations
Birth weight, gestational age, Apgar score at 5 minutes, head circumference, stillbirth	Danish Medical Birth Registry Finnish Medical Birth Register* Medical Birth Registry of Norway Swedish Medical Birth Register	A specific variable in each birth registry	
Neurodevelopmental outcomes	Danish National Patient Registry ⁴³ Danish Psychiatric Central Research Register ⁴⁷ Danish Psychiatric Central Register Finnish Care Register for Health Care Finnish Register of Primary Health Care visits Norwegian Patient Registry ^{48±} Swedish National Patient Register ^{29,49} Danish National Health Services Prescription Database ^{45,46} Finnish Prescription Register ⁴⁵ Norwegian Prescription Database ⁴⁵ Swedish Prescribed Drug Register ⁴⁵	ICD-10 for diagnoses, ATC codes for drug proxies	
Characteristic of study population and covariates (for full list see Section 8.3.3)	Mother: age, parity, marital/cohabiting status, mode of delivery, smoking during pregnancy, BMI	Danish Medical Birth Registry Finnish Medical Birth Register* National Registry of Norway ⁵⁰ Swedish Medical Birth Register ⁴²	A specific variable in each birth registry
	Offspring: sex, multiplicity of gestation		

Table 3. National registries in Denmark, Finland, Norway and Sweden and type of data available from each registry

Study variable/role	Type of data	Data source(s)	Coding system(s) used
Maternal morbidity (including indication for pregabalin) Markers of health care utilisation		Danish National Patient Registry, ⁴³ Finnish Care Register for Health Care Finnish Register of Primary Health Care visits Norwegian Patient Registry ⁴⁸ Swedish National Patient Register ^{29,49}	ICD-10 for diagnoses, ATC for medication proxies
		Danish National Health Services Prescription Database ^{45,46} Finnish Prescription Register ⁴⁵ Norwegian Prescription Database ⁴⁵ Swedish Prescribed Drug Register ⁴⁵	
Maternal medications		Danish National Health Services Prescription Database ^{45,46} Finnish Prescription Register ⁴⁵ Norwegian Prescription Database ⁴⁵ Swedish Prescribed Drug Register ⁴⁵	ATC
Loss to follow-up		Danish Civil Danish Civil Registration System ⁴¹	A specific variable in each registry
Death, emigration [†]		Finnish Causes of Death Register Finnish Population Register Centre National Registry of Norway Swedish Cause of Death Register	

*Data for the Medical Birth Register, the Register on Induced Abortions, the Malformation Register and the Prescription Register (3 months before last menstrual period) can be obtained from the Finnish Drugs and Pregnancy Project (DPP) database.

[†]Emigration data not available in the Swedish or the Norwegian dataset

[‡]Data available from 2008 onwards in Norway

8.5. Study size

Table 4 shows estimated number of total pregnancies ending in live or stillbirth and pregnancies with exposures and indications potentially relevant for analysis.

Table 4. Estimated numbers of pregnancies ending in live or still birth for potentially analysis-relevant categories

	Denmark (2005-2016)	Finland (2005-2014)	Norway* (2005-2016)	Sweden (2006-2013)
Pregnancies ending in live/still birth	730,000	580,000	650,000	800,000
Pregnancies with dispensation of				
Pregabalin, first trimester	200	700	200	400
Pregabalin, any time during pregnancy	350	900	350	800
Lamotrigine, first trimester	2000	900	2000	1300
Lamotrigine, any time during pregnancy	2700	1100	2700	1800
Duloxetine, first trimester	400	500	400	500
Duloxetine, any time during pregnancy	800	600	800	1000

*Pilot data not available; estimated based on pilot data from Denmark due to similar s population size.

The estimated numbers of pregnancies ending in live or still birth for potentially analysis-relevant categories for Norway were unavailable at the time of the protocol writing but are estimated in Table 4 by imputing data from Denmark, where the number of pregabalin users was the lowest, to provide the most conservative estimate. Based on this and on each country’s population size, conservatively estimated achievable size for this study will be more than 1000 pregnancies exposed to pregabalin during the first trimester.^{20,51} Table 5 shows the maximum upper limit of the 95% confidence interval of risk ratio that can be ruled out with 80% probability, for different scenarios with respect to the size of the exposed and comparator groups conservatively assuming N=1000 to be the size of pregabalin-exposed pregnancies. This analysis assumes that the true underlying risk ratio is 1.0 (no association between pregabalin exposure and an endpoint). For example, assuming the background prevalence of major congenital malformations to be 3%, underlying pregabalin-associated RR, and allocation ratio of comparator to pregabalin of 119:1 (corresponding to pregabalin exposure prevalence 0.8%), the analysis will rule out a RR with an upper confidence limit of 1.65845.

Table 5. Maximum upper limits of 95% confidence interval for risk or prevalence ratios depending on the prevalence of selected outcomes representative of prevalence of various study outcomes

Outcome	Estimated prevalence of outcome	Maximum upper limit of 95% confidence interval for risk ratio can be ruled out with at least 80% probability (unexposed:exposed allocation ratio= 119:1; approximate the analysis with pregabalin-unexposed as a comparator*)
Malformations of the nervous system ^{20,45} , mental retardation	0.2%	7.2
Stillbirth, postnatal outcomes, ASD	0.6%	3.1
Cardiac congenital malformations, postnatal outcomes ^{18,20} , ADHD	1%	2.4
Any major congenital malformation ^{18,20}	3%	1.7
Preterm birth/SGA	10%	1.3

Assumes true risk ratio =1.0, size of the pregabalin-exposed group N=1000 for first-trimester exposure and N=1000 for any exposure in pregnancy with minimum 6 years follow-up.

*The expected size of the pregabalin-unexposed pregnancies is about ten-fold of that used in the above calculations and the size of the pregabalin-exposed group during pregnancy is expected to be larger than that exposed in the first trimester. The computations were done using SAS software based on the ‘Study size’ worksheet of the Episheet.⁵²

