8.7. Data analysis

All steps of the country-specific data analyses will be conducted separately in each participating country according to the description below. Each country will generate a set of identical analytic tables, according to the table shells, provided in [Annex 3](#).

After conducting the country-specific data analyses, country-specific datasets containing crude and adjusted estimates of association will be transferred to Aarhus University Hospital, Denmark, for meta-analyses.

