8.7.3. Estimation of prevalence ratios and hazard ratios

Crude and adjusted prevalence ratios and 95% Wald confidence intervals (CIs) for each birth outcome and a given population/contrast will be estimated using log-binomial regression.

Crude and adjusted incidence rate ratios and 95% Wald CIs will be estimated Cox's proportional-hazards regression for each postnatal outcome.

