8.7.7. Meta-analyses

After the separate analyses in each participating country as specified in the tables in [Annex 3](#), aggregated level data on crude and adjusted estimates of association will be transferred to Aarhus University Hospital, Denmark for meta-analyses. Because of the similarities between the healthcare systems in the Nordic countries and the use of a common study protocol with well-defined selection of exposures, outcomes and covariates, the MAH does not expect the associations between the exposures and outcomes to vary substantially between countries and therefore a fixed-effects meta-analysis will be applied.⁵⁶ Country-specific crude and adjusted estimates of association for each prespecified contrast will be combined in a meta-analysis.⁵⁷ For each outcome the MAH will use the inverse variance method in the fixed effects meta-analyses, which is weighting the country-specific estimates of association by the inverse of the within-country variances. Heterogeneity of the estimates will be verified and a random-effects meta-analysis will be considered as an alternative should the estimates be found to vary significantly between countries. Results of the meta-analyses will be presented using a standard forest plot, reporting the country-specific overall crude and adjusted point estimates, and the pooled overall point estimate, all with 95% CIs.

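### Table 5's 80% assurance is calculated for one combined table, but the plan pools four country estimates; at the stated N=1000 the 0.6% and 1% rows fall short and the 0.2% row depends on an unstated zero-case rule

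*Protocol*

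**What the plan says.** Protocol section 8.5 states the study's precision by "conservatively assuming N=1000 to be the size of pregabalin-exposed pregnancies". It adds: "This analysis assumes that the true underlying risk ratio is 1.0". The worked example has a 3% outcome and an "allocation ratio of comparator to pregabalin of 119:1", and arrives at 1.65845. Table 5 prints 7.2, 3.1, 2.4, 1.7 and 1.3 for prevalences of 0.2%, 0.6%, 1%, 3% and 10%. Its column is headed "Maximum upper limit of 95% confidence interval for risk ratio can be ruled out with at least 80% probability", and its note names an Episheet worksheet as the source. No country term appears.

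The analysis is laid out differently. Section 8.7: "All steps of the country-specific data analyses will be conducted separately in each participating country". Section 8.7.3: "95% Wald confidence intervals (CIs) for each birth outcome and a given population/contrast will be estimated using log-binomial regression". Under section 8.6, individual records from Finland, Norway and Sweden are not released to the coordinating centre. Under section 8.7.7 the country estimates are combined by "weighting the country-specific estimates of association by the inverse of the within-country variances". The protocol does not say how a country with no exposed case enters the pooling.

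**The concern.** Table 5 is the protocol's only statement of which risk ratios the study can exclude. It is worked out for a combined table that will never be analysed. With common outcomes the difference hardly matters. With rare ones, 1000 exposed pregnancies spread over four countries leave some countries with no exposed case, so they have no finite log prevalence ratio. If they drop out, the countries that remain are those in which a case happened to occur. The pooled ratio then drifts upward and the interval widens.

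The affected rows include nervous-system malformations, stillbirth and cardiac malformations. If the exposed group ended near the planning minimum, a wide or raised pooled interval could be misread as chance or as a signal, because the protocol had promised a precision that the planned analysis does not give at that size.

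**Working it through.** **Inputs (Protocol section 8.5).** Exposed N=1000; 119 comparators per exposed; true risk ratio 1.0; Table 5 prevalences and limits; Table 4 pregabalin counts for Denmark, Finland, Norway and Sweden: first trimester 200, 700, 200, 400 (sum 1500), any time 350, 900, 350, 800 (sum 2400). Scaling 1500 to 1000 gives 133, 467, 133, 267. Using these shares at N=1000 is my assumption.

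**Step 1: reproduce Table 5.** For one table, SE = sqrt[((1−p)/p) × (1/1000 + 1/119000)] and limit = exp[(1.96 + 0.8416) × SE].

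| p | SE | Limit | Printed |
|---|---|---|---|
| 0.2% | 0.7094 | 7.30 | 7.2 |
| 0.6% | 0.4087 | 3.14 | 3.1 |
| 1% | 0.3160 | 2.42 | 2.4 |
| 3% | 0.1806 | 1.658 | 1.7 (text 1.65845) |
| 10% | 0.0953 | 1.306 | 1.3 |

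The arithmetic is right for a single table. Simulating that table with a Wald interval meets the printed limits with probability 86%, 93%, 91%, 90% and 82%.

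**Step 2: how sparse the countries are.** Expected exposed cases (country size × p):
- 0.2%: 0.27, 0.93, 0.27, 0.53
- 0.6%: 0.80, 2.80, 0.80, 1.60
- 1%: 1.33, 4.67, 1.33, 2.67

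The probability that at least one country has none is 1 − Π[1 − (1−p)^n]: about 99%, 77% and 50%. The probability that no country has any at 0.2% is 0.998^1000 ≈ 13%.

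**Step 3: simulate the planned pooling.** Binomial counts per country; log ratio with variance 1/a − 1/n1 + 1/b − 1/n0 (a and b the exposed and comparator cases, n1 and n0 the group sizes); inverse-variance fixed-effect pooling; success if the pooled upper limit is below the printed value. At least 100,000 replicates per scenario. N=1000:

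| Row (limit) | Zero-case countries dropped: P; 80% limit | 0.5 added in those countries: P; 80% limit |
|---|---|---|
| 0.2% (7.2) | 22%; about 24 | 89%; about 6.4 |
| 0.6% (3.1) | 55%; 3.7 | 74%; 3.2 |
| 1% (2.4) | 66%; 2.6 | 74%; 2.5 |
| 3% (1.7) | 82%; 1.69 | 82%; 1.68 |
| 10% (1.3) | 77%; 1.31 | 77%; 1.31 |

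With zero-case countries dropped, the median pooled ratio in the first three rows is about 2.2, 1.33 and 1.18, although the truth is 1.0.

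**Step 4: vary the assumptions at N=1000.** With zero-case countries dropped, other country splits and Table 4 births as comparators give 12–22%, 49–56% and about 66% for the first three rows. A comparator of 1190:1 gives 18%, 56% and 66%, so exposed cases are the limiting factor. Adding 0.5 in every country gives 72–76%, 54–56% and 57–58%. The 0.6% and 1% rows stayed below 80% in every variant.

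**Step 5: Table 4's sizes, zero-case countries dropped.**

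| Row | N=1500 | N=2400 |
|---|---|---|
| 0.2% | 73% | 97% |
| 0.6% | 91% | 99.8% |
| 1% | 93% | 99.8% |
| 3% | 97% | 99.9% |
| 10% | 93% | 99% |

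At N=1500 the 0.2% row rises to about 99% with 0.5 added in zero-case countries.

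**The case against.** The strongest reply is that N=1000 is a floor. Section 8.5 expects more than that, Table 4 sums to 1500 and 2400, and the Table 5 note says the any-trimester group will be larger than the first-trimester one. All outcomes in the 0.6% row use any-trimester exposure, so their matching size is 2400, where the limit is met almost surely. This stands. A reader might infer from Step 3 that the study cannot exclude the printed ratios for stillbirth or cardiac malformations; at the protocol's expected sizes it can. It does not rescue the statement as printed, because Table 5 attaches its probability explicitly to N=1000 for both exposure windows.

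Second, zero-case handling may properly sit in an analysis plan that is not shown. This also stands, and it is why neither 22% nor a limit of 24 should be quoted for the 0.2% row without its condition. It does not rescue the 0.6% and 1% rows, which miss under each convention tried.

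Third, the column is labelled an approximation, specific malformation types are analysed only where numbers permit (section 8.7.4.1), and section 8.7.5 falls back on counts and crude rates for sparse postnatal outcomes. Those provisions soften the consequence for the rarest outcomes. They do not cover stillbirth, and a column promising at least 80% should not err on the favourable side.

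**Conclusion.** The concern holds in a limited form. Table 5 is correct arithmetic for a different analysis from the one planned. At its stated N=1000, the 80% assurance is missed in the 0.6% row (55–74%) and the 1% row (66–74%), depending on whether zero-case countries are dropped or given 0.5. The limits met with 80% probability are about 3.2–3.7 and 2.5–2.6, against 3.1 and 2.4. The 0.2% row is undetermined until the zero-case rule is known. The printed 3% limit of 1.7 holds, although the unrounded 1.658 would be met only about 76% of the time. The 10% row should not be pressed: its 80% limit of 1.31 still prints as 1.3.

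At Table 4's sizes the only shortfall is first-trimester nervous-system malformations, about 73% if zero-case countries are dropped. A reader might also infer that *conservatively* is misused in section 8.5. It is not: it describes choosing 1000 against an expected 1500 or 2400.

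The figures assume Table 4's country shares, with Norway's counts imputed from Denmark's. They are unadjusted and treat every outcome as a proportion, so propensity-score trimming and weighting and the Cox models are not represented.

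**What to change.** Recompute Table 5 by simulation under a risk ratio of 1 for the planned analysis: four country Wald estimates at Table 4's country shares, pooled as in section 8.7.7. State the zero-case convention used, and where countries are dropped give the probability that no pooled estimate exists (about 13% at 0.2% prevalence and N=1000). Print the limits at N=1000 and at Table 4's expected sizes, using 1500 for first-trimester outcomes and 2400 for any-trimester outcomes. Keep *conservatively* for the choice of N, but do not claim at least 80% at N=1000 for rows that miss it.

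The cost is a short simulation and revised text in section 8.5, with no change to data, conduct or analysis. The drawback is a less favourable stated precision for rare outcomes at N=1000.

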8.3.2.1. Primary Outcomes (Birth outcomes)

- Major congenital malformations, any and specific, according to the European Network of Congenital Anomaly Registers (EUROCAT) classification²⁰
- Stillbirth, as recorded in each country's birth registry
- Low birth weight (birth weight < 2500 g)
- Small for gestational age (SGA), defined, for singleton pregnancies, as a dichotomous variable (yes/no) of birth weight below 2 standard deviations (SDs) of sex- and gestational week specific distributions, using country-specific reference standard.^{19,21} SGA non-singleton gestations will be defined if appropriate reference standard can be defined/identified; otherwise set to missing.
- Preterm birth, defined as gestational age <37 weeks
- Low Apgar score at 5 minutes, defined as a dichotomous variable (score 0-6 vs. score 7-10)
- Microcephaly, defined as a dichotomous variable (yes/no) of head circumference at birth (cm) smaller than 2 SD of sex- and gestational week specific distribution, using country-specific reference standard

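### Table 5 places SGA in the 10% prevalence row (upper limit 1.3), but the protocol's 2-SD definition implies about 2.3% and an upper limit of about 1.8

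*Protocol*

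**What the plan says.** SGA is one of the primary birth outcomes. Section 8.3.2.1 of the protocol defines it for singletons, as a yes/no variable, by "birth weight below 2 standard deviations (SDs) of sex- and gestational week specific distributions, using country-specific reference standard". No other SGA cut-off appears anywhere in the protocol. Section 8.7.4 assesses SGA in live births, with exposure at any time in pregnancy.

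Section 8.5 says that Table 5 shows "the maximum upper limit of the 95% confidence interval of risk ratio that can be ruled out with 80% probability". It adds: "This analysis assumes that the true underlying risk ratio is 1.0". The last row of Table 5 is "Preterm birth/SGA", with prevalence 10% and limit 1.3. The row cites no source. The table note gives the "size of the pregabalin-exposed group N=1000 for first-trimester exposure and N=1000 for any exposure in pregnancy", and the worked example in the text uses an "allocation ratio of comparator to pregabalin of 119:1".

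**The concern.** The two sections do not describe the same outcome. A 10% prevalence would fit a 10th-percentile cut-off. A cut-off 2 SD below the reference mean picks out a much smaller tail. Because precision at a fixed sample size depends strongly on prevalence, the limit of 1.3 attached to SGA does not follow from the SGA that the study will measure.

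The study is a safety commitment to the EMA, and Table 5 is where the protocol says what it could exclude. As printed, SGA shares the most precise row of the table. Under the 2-SD definition it would be less precise than the 3% row for any major malformation. A null SGA result could then be read as more reassuring than the planned size supports.

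**Working it through.** **Inputs**

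- Two-sided 95% interval, z = 1.960, and 80% probability, z = 0.8416 (section 8.5 and Table 5 column heading). The sum is 2.8016.
- True risk ratio 1.0; n = 1000 exposed; k = 119 unexposed per exposed (section 8.5, Table 5).
- Any-trimester exposed in Table 4: 350 + 900 + 350 + 800 = 2400.
- SGA prevalence under the 2-SD definition: P(Z < −2) = 0.02275, or 2.28%. This is a normal-theory assumption, so a range of 2% to 5% is shown as well.

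**Formula**

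SE = √[ (1 − p)/(n·p) × (1 + 1/k) ], and upper limit = exp(2.8016 × SE).

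**Reproducing the protocol's figures**

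- p = 3%: SE = √(0.97/30 × 1.0084) = 0.1806, so the limit is exp(0.5059) = 1.6584. The worked example in section 8.5 prints 1.65845, which identifies the method.
- p = 10%: SE = √(0.90/100 × 1.0084) = 0.0953, so the limit is exp(0.2669) = 1.306, printed as 1.3.
- The rows at 0.2%, 0.6% and 1% come out at 7.30, 3.14 and 2.42, against 7.2, 3.1 and 2.4 in Table 5.

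**SGA at the 2-SD prevalence**

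- p = 2.28%, n = 1000: SE = √(0.97725/22.75 × 1.0084) = 0.2081, so the limit is exp(0.5831) = 1.79.
- p = 2.28%, n = 2400: SE = √(0.97725/54.6 × 1.0084) = 0.1343, so the limit is exp(0.3764) = 1.46.
- p = 2.28%, n = 1000, with ten times as many unexposed (1190:1): 1.79, unchanged to two decimals.

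**Range over assumed prevalence (119:1)**

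| SGA prevalence | Limit, n = 1000 | Limit, n = 2400 |
|---|---|---|
| 2% | 1.86 | 1.49 |
| 2.28% | 1.79 | 1.46 |
| 2.5% | 1.74 | 1.43 |
| 3% | 1.66 | 1.39 |
| 4% | 1.55 | 1.32 |
| 5% | 1.47 | 1.28 |
| 10% | 1.31 | 1.19 |

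**Probability that the upper limit falls below 1.3**

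This is Φ(ln 1.3/SE − 1.960), with ln 1.3 = 0.2624.

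- p = 10%, n = 1000: about 79%, in line with the intended 80% once 1.306 is rounded.
- p = 2.28%, n = 1000: Φ(1.261 − 1.960) = Φ(−0.699), about 24%.
- p = 2.28%, n = 2400: Φ(1.953 − 1.960) = Φ(−0.007), about 50%.

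**Exposed pregnancies needed for a limit of 1.3 at 2.28%**

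n = 2.8016² × (0.97725/0.02275) × 1.0084 / 0.2624², about 4900. This is roughly twice the any-trimester total in Table 4.

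**The case against.** The strongest reply is that 2.28% is not in the protocol. The share of the cohort below 2 SD depends on the country-specific reference, its age and the skewness of birth weight. That stands, and it is why a range is given. The reply can be taken further: SGA uses any-trimester exposure, the N of 1000 is conservative by the protocol's own account, and with 2400 exposed the limit is 1.32 at 4% and 1.28 at 5%. In that combination the printed 1.3 would roughly hold. So a reader should not infer that a limit of 1.3 is impossible for SGA. But Table 5 is computed at 1000 for any exposure, and nothing in the protocol supports a prevalence of 4% to 5% for a 2-SD cut-off.

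Three other strong readings are not supported:

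- **Table 5 is miscalculated.** It is not: 1.3 follows from 10%. The fault is the prevalence assigned to SGA.
- **Microcephaly, also defined by 2 SD, is wrongly left out.** Table 5 covers selected representative outcomes, and low birth weight and low Apgar score have no row either.
- **The analysis is compromised.** All eligible registry pregnancies are included, Table 5 sets no recruitment target or success threshold, and the report will show the actual SGA interval.

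It may also be said that the table's prevalences are only representative. However, the table names SGA in the 10% row, while the 3% row is much closer to a 2-SD definition.

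**Conclusion.** The point holds as an inconsistency between the SGA definition and the prevalence assigned to SGA in the study-size table. If the 2-SD definition is right, the precision stated for this primary outcome is too favourable: about 1.8 rather than 1.3 at the protocol's own N of 1000, and about 1.46 with every any-trimester exposed pregnancy in Table 4. These figures rest on a normal-theory prevalence of 2.28%. Over 2% to 5% the limit at N = 1000 runs from 1.86 to 1.47, so it stays above 1.3 throughout. They also assume a true risk ratio of 1.0 and ignore the restriction of SGA to singletons, which would widen the limit slightly. The limit is a precision bound under no association, not a detectable effect. The consequence is confined to a planning statement for one outcome, but it is a stated figure that the design does not deliver under its own definition.

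**What to change.** Take SGA out of the 10% row and give it its own row, with a prevalence that matches the 2-SD definition (about 2% to 3%), the source of that prevalence, and the recomputed limit (about 1.7 to 1.9 at N = 1000). If the any-trimester count is used instead of 1000, say so in the row. Alternatively, if a percentile cut-off was intended, reconcile section 8.3.2.1 with the 10% figure so that outcome and table agree. Leave preterm birth as it is. The cost is one table row and a less favourable stated precision for SGA; with the 2-SD definition kept, no analysis, population or data request changes.
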